9.3 Primary Efficacy Endpoint and Analyses

9.3.1 Primary Efficacy Endpoint

The primary endpoint is the proportion of subjects achieving HiSCR at Week 16 as defined in Section 3.1.

9.3.2 Main Analysis of Primary Efficacy Endpoint

The corresponding statistical null hypothesis to the primary endpoint is that there is no difference between each risankizumab dose and placebo, in the proportion of subjects achieving HiSCR at Week 16.

Comparison of the primary endpoint will be made between each risankizumab dose and placebo using the Cochran-Mantel-Haenszel (CMH) test, adjusting for the actual values stratification factors under a two-sided alpha level 0.025 for each dose.

The attributes of the estimand corresponding to the primary efficacy endpoint is summarized in Table 2.

Table 2. Summary of the Estimand Attributes of the Primary Efficacy Endpoint

	Attributes of the Estimand					
Estimand	Treatment	Endpoint	Population	Intercurrent Events	Statistical Summary	
Primary efficacy endpoint of HiSCR at Week 16	Risankizumab 180 mg / risankizumab 360 mg / Placebo	Achievement of HiSCR at Week 16 without the initiation of any antibiotics for HS-related infections and without discontinuation of study drug due to lack of efficacy	Patients with moderate to severe HS	The intercurrents of either initiation of any antibiotics for HS-related infections or discontinuation of study drug due to lack of efficacy are included in the endpoint attribute using composite variable strategy. No other intercurrent event is considered.	Difference in proportion of subjects achieving HiSCR at Week 16 between each risankizumab dose and placebo	

NRI-C will be the primary approach to handle missing data.

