2.3 Treatment Assignment and Blinding

All subjects will be assigned a unique identification number by the interactive response technology (IRT) system at the screening visit. For subjects who rescreen, the screening number assigned by the IRT at the initial screening visit should be used. The IRT will assign a randomization number that will encode the subject's treatment group assignment according to the randomization schedule generated by the statistics department at AbbVie.

Subjects who meet the study's eligibility criteria will be initially randomized to receive either risankizumab 180 mg or 360 mg as an SC injection or matching placebo up to Week 16 in a 1:1:1 ratio.

Subjects who have been treated with anti-TNF therapy and had inadequate response to this therapy (TNF- IR) will be eligible. Subjects will be randomized by their anti-TNF use (yes or no) prior to Baseline. TNF-naïve (no) subjects will be further stratified by the worst Hurley stage across all affected anatomic regions. Therefore, there will be 4 strata in total:

- Prior exposure to anti-TNF (yes)
- Prior exposure to anti-TNF (no) with the worst Hurley Stage as I
- Prior exposure to anti-TNF (no) with the worst Hurley Stage as II
- Prior exposure to anti-TNF (no) with the worst Hurley Stage as III

All AbbVie personnel of the study (with the exception of AbbVie Drug Supply Management Team) will remain blinded until the Primary Analysis at Week 16 is available. The investigator, study site personnel, and the subject will remain blinded to each subject's initial treatment throughout the study. To maintain the blind, the risankizumab kits and placebo kits provided for the study will be identical in appearance. The IRT will provide access to unblinded subject treatment information in the case of a medical emergency.

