3.1 Primary Endpoint

The primary endpoint is the proportion of subjects achieving HiSCR at Week 16. HiSCR is defined as at least a 50% reduction in the total AN count with no increase in abscess count and no increase in draining fistula count relative to Baseline.

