9.1 General Considerations

All efficacy analyses will be conducted in the ITT Population. In addition, Per-protocol analysis for primary endpoint will be performed. All statistical tests, between each risankizumab dose and placebo, will be performed at a two-sided alpha level of 0.025.

The Primary Analysis will be performed after the last ongoing subject has completed the Week 16 visit, and the data up to Week 16 have be cleaned. This will be the only and final analysis for the primary and ranked secondary endpoints. Study sites and subjects will remain blinded to their initial treatment assignment for the duration of the entire study.

For categorical endpoints, comparisons will be made between each risankizumab dosing group and placebo using the Cochran-Mantel-Haenszel (CMH) test, adjusting for the actual values of stratification factors. In case of any stratum with zero subject in either treatment group, no stratification factor will be controlled. Non-responder imputation (NRI) will be the primary approach to handle missing values. To account for the impact of COVID-19 pandemic, the NRI will be adjusted to NRI-C, Non-Responder Imputation incorporating multiple imputation to handle missing data due to COVID-19.

For continuous endpoints, comparisons will be made between each risankizumab dosing group and placebo based on the fixed term of treatment from a Mixed-effect Model

[figure not shown]
Repeat Measurement (MMRM) model including the Baseline value and observed measurements at all post-baseline visits, adjusting for the fixed effects of treatment, actual values of stratification factors, visit and treatment-by-visit interaction as covariates. The MMRM will be the primary approach to handle missing values.

For variables other than PGA Skin Pain NRS and HSSA, "Baseline" refers to the last non-missing observation on or before the date of the first administration of study drug or the date of randomization if no study drug is given. The "Baseline" of PGA Skin Pain NRS and HSSA is defined as the last non-missing weekly average score, calculated based on the daily scores from the past 7 days, on or before the date of the first administration of study drug or the date of randomization if no study drug is given. For variables where the assessment time is collected on the ePRO device, the baseline measurement must be prior to the time of the first administration of study drug.

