9.6 Efficacy Subgroup Analyses

To evaluate the consistency of the efficacy over demographic and other baseline characteristics, analyses will be performed for the following subgroups for the primary efficacy endpoint.

- Age group ($< 40 \text{ years}, \ge 40 < 65 \text{ years}, \ge 65 \text{ years}$)
- Sex (male, female)
- Race (white, non-white)
- Smoking (current, ex or never)
- BMI (normal: < 25, overweight: $\ge 25 < 30$, obese: ≥ 30)
- Duration of HS (by median)
- Baseline body weight (by median)
- Baseline CRP level (by median)
- Baseline AN count category (5-10, 11+)
- Prior exposure to TNF antagonists (yes, no)
- Prior exposure to biologic agents that block IL-12/23/17 (yes, no)
- Baseline Hurley stage (I, II, III)

In addition, the primary efficacy endpoint may also be summarized by anti-drug antibody (ADA) status and/or by neutralizing antibody (NAb) status, once the corresponding ADA and NAb data are completed.

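### The primary HiSCR test adjusts for the TNF/Hurley strata only; pre-specified adjustment for Baseline lesion counts would be a cheap and probably modest gain in precision

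*SAP*

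**What the plan says.** SAP 9.3.2 tests the primary endpoint "using the Cochran-Mantel-Haenszel (CMH) test, adjusting for the actual values stratification factors", at two-sided 0.025 per dose. Protocol 7.3 also names the CMH test with adjustment for stratification factors. The sample code in SAP Appendix E computes a Mantel-Haenszel risk difference by stratum and uses no other covariate.

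SAP 2.3 defines the strata. Anti-TNF-exposed subjects form one stratum, and anti-TNF-naive subjects are "further stratified by the worst Hurley stage across all affected anatomic regions", which gives four. SAP 9.1 adds a fallback: "In case of any stratum with zero subject in either treatment group, no stratification factor will be controlled".

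HiSCR itself is defined from changes in lesion counts since Baseline (SAP 3.1): "at least a 50% reduction in the total AN count with no increase in abscess count and no increase in draining fistula count". The summary measure in SAP Table 2 is a risk difference: "Difference in proportion of subjects achieving HiSCR at Week 16 between each risankizumab dose and placebo".

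Elsewhere the SAP does use Baseline values:
- The imputation models (9.2.1 and Appendix E) include the Baseline count of the lesion type being imputed, anti-TNF exposure and worst Hurley stage for all subjects.
- Every MMRM includes the Baseline measurement (9.2.2).
- SAP 9.6 plans a subgroup analysis of HiSCR by Baseline AN count (5-10 versus 11 or more).

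SAP 9.3.3 plans an MI analysis and a per-protocol analysis of the primary endpoint. Neither adds a covariate to the test.

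**The concern.** Baseline abscess, nodule and draining fistula counts are measured on entry and are natural candidates as predictors of HiSCR. Because counts are whole numbers, even the size of the hurdle varies: a subject with AN 5 must fall to 2 (a 60% drop), while one with AN 6 need only fall to 3 (50%). Entry allows any AN count from 5 upwards and 0 to 20 draining fistulas, so severity can vary widely within a stratum.

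If these counts are prognostic beyond the strata, a test that leaves them out has a larger standard error than it needs. It also leaves chance imbalance in lesion burden between arms of 74 uncorrected. The stakes are highest for 180 mg, where power is lowest, because a dose that misses on HiSCR cannot go on to its seven ranked secondary endpoints (SAP 9.4.2 and 13.0).

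**Working it through.** **Inputs (SAP 2.4, Table 1).** 74 per arm; two-sided alpha 0.025 per dose, so the critical value is 2.2414; placebo 26%; 360 mg 53%; 180 mg 39.5%, 46.5% or 50% under the linear, EMax and early-plateau models. The stated power for at least one dose is 83.9%, 87.6% and 90.6%.

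**Step 1: reproduce the stated power.** With a shared placebo arm, power for at least one dose = 1 − Σₓ Bin(x; 74, 0.26) × [1 − r180(x)] × [1 − r360(x)]. Here r(x) is the chance that a dose is significant when placebo has x responders.

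| Test | Linear | EMax | Early plateau |
|---|---|---|---|
| SAP Table 1 | 83.9% | 87.6% | 90.6% |
| Continuity-corrected chi-square | 84.5% | 88.0% | 91.0% |
| Fisher exact | 84.8% | 88.2% | 91.1% |
| Uncorrected chi-square | 88.5% | 91.4% | 93.7% |

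The plan's figures behave like a conservative, unstratified two-proportion test. They take no credit for covariates, so the design does not depend on adjustment.

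**Step 2: effect of adjustment on power.** Let R² be the share of HiSCR variance that the counts explain beyond the strata. The documents give no value, so it is assumed. Multiply both standard errors by f = √(1 − R²):

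power = Φ{[(p − p₀) − 2.2414·f·s₀] / (f·s₁)}, with s₀ = √[2p̄(1 − p̄)/74] and s₁ = √{[p₀(1 − p₀) + p(1 − p)]/74}.

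For 360 mg, p̄ = 0.395, s₀ = 0.0804 and s₁ = 0.0772.
- R² = 0: (0.27 − 0.1801)/0.0772 = 1.163, power 87.8%.
- R² = 0.10: f = 0.9487, (0.27 − 0.1709)/0.0733 = 1.353, power 91.2%.

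The corrected columns subtract 1/74 from the difference, which is closer to the SAP's own scale.

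| Assumed R² | 360 mg | 180 mg (EMax) | 360 mg, corrected | 180 mg (EMax), corrected | 222 × (1 − R²) |
|---|---|---|---|---|---|
| 0 | 87.8% | 64.1% | 83.9% | 57.4% | 222 |
| 1% | 88.1% | 64.6% | 84.3% | 57.9% | 220 |
| 5% | 89.5% | 66.6% | 85.9% | 59.9% | 211 |
| 10% | 91.2% | 69.3% | 87.9% | 62.6% | 200 |

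The levels depend on the approximation. The uncorrected 87.8% for 360 mg alone exceeds the SAP's 83.9% for either dose in the linear scenario, so it is not on the SAP's scale. Exact enumeration with the continuity correction gives 83.6% for 360 mg and 57.2% for 180 mg. The differences are more stable: about 0.3 to 0.4, 1.7 to 2.0 and 3.4 to 4.0 points for 360 mg, and 0.5, 2.5 and 5.2 points for 180 mg. The last column is the sample size that, with adjustment, matches the precision of 222 without it.

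**Step 3: what such an R² would require.** Assume a 50/50 split between AN 5-10 and AN 11 or more, and response rates of 26% and 53%. The mean binomial variance is (0.1924 + 0.2491)/2 = 0.2208. If response differs by d between the AN groups, R² = 0.25d²/0.2208.
- d = 10 points: 0.0025/0.2208 = 0.011
- d = 20 points: 0.0100/0.2208 = 0.045
- d = 30 points: 0.0225/0.2208 = 0.102

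**Step 4: cost if the counts predict nothing.** Trials were simulated at 74 per arm, with a standardised risk difference from a logistic model containing pure-noise covariates. One covariate inflated the variance by about 0.6% to 0.7% when two arms were fitted. Three covariates inflated it by about 2.1% with two arms and about 1.3% when all three arms were fitted together. A 2% inflation lowers the uncorrected power from 87.8% to 87.1% for 360 mg and from 64.1% to 63.1% for 180 mg. The gains in step 2 are before this cost, so three counts break even at an R² of roughly 1% to 2%.

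**The case against.** The strongest reply is that nothing here is wrong. The stratified CMH test is valid, follows the randomisation and delivers the risk difference in Table 2. The stated power is met without covariates. All of this stands.

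A reader might go further and infer that precision is certainly being lost, or that adjustment is free. The documents support neither. They give no association between Baseline counts and HiSCR. HiSCR is already scaled to Baseline, and Hurley stage may already carry part of the severity. Being part of a response definition does not make a Baseline count prognostic. The AN subgroup in SAP 9.6 is one of twelve routine consistency checks and is no evidence of prognosis either. Nor does the SAP disregard Baseline counts as a whole, since the imputation models use them.

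The practical objections also stand, but they can be met:
- CMH is written into protocol 7.3, and protocol 8.1 requires ethics review of any amendment.
- SAP 9.2.1 keeps subjects with a missing Baseline in the analysis, whereas a regression would drop them without a further rule.
- The per-protocol definition restates AN ≥ 5 as a filter, so the ITT set may hold subjects below 5, and the log of zero is undefined.
- A logistic model can separate or fail to converge in some imputations.
- Adjusting for stratum alone would leave Hurley stage unused in TNF-exposed subjects.

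These points shape the fix and its cost. They do not remove the case for it.

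**Conclusion.** The point holds as an optional efficiency gain. The primary HiSCR test uses no Baseline lesion count, and no Hurley stage among TNF-exposed subjects, although both are collected. For an assumed R² of 1%, 5% and 10% beyond the strata, the power gain is about 0.3, 1.7 and 3.5 points for 360 mg and about 0.5, 2.5 and 5 points for 180 mg under EMax. An R² of 10% needs a strong association, around a 30-point difference in response between AN groups. If the counts are not prognostic, the cost is under 1% in variance for one count and about 1% to 2% for three.

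The result rests on the assumed R² range, the SAP's response rates, 74 evaluable subjects per arm and a normal approximation. The validity of the CMH test is not in question.

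**What to change.** Before unblinding, add to SAP 9.3 a standardised (marginal) risk difference from a logistic model. The covariates are treatment, prior anti-TNF exposure, worst Hurley stage in all subjects, log(Baseline AN count + 1), Baseline abscess count and Baseline draining fistula count. Use a robust standard error and combine over the 30 imputations by Rubin's rules, as now. Fitting all three arms in one model keeps the cost of extra covariates down. The Table 2 summary measure does not change.

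State three rules with it:
- For a missing Baseline count, fill the covariate only (for example with the overall mean) and leave HiSCR status as SAP 9.2.1 sets it.
- If the model separates or does not converge, fall back to the stratified CMH analysis.
- Do not add AN category as a further CMH stratum. More cells make the empty-stratum rule in SAP 9.1, which drops all adjustment, more likely to apply.

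There are two ways to place it. As the primary estimate, with CMH as a sensitivity analysis, it needs a matching edit to protocol 7.3 and the ethics review that goes with an amendment. As a named supplementary analysis in SAP 9.3.3, it needs SAP text only.

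Label: cheap improvement. The cost is a SAP edit, a short program, possibly a protocol wording change, and a small loss of precision if the counts turn out not to be prognostic. No new data are needed.

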9.3.3 Sensitivity and Supplementary Analyses of the Primary Efficacy Endpoint

A sensitivity analysis using MI to handle missing data will be performed on the primary endpoint, as defined in Section 9.2.1.

The primary endpoint will also be analyzed among a PP population as additional sensitivity analyses, using the same approaches to handle missing data.

The attributes of the estimand corresponding to the sensitivity analysis of the primary efficacy endpoint among the PP Population is summarized in Table 3.

[figure not shown]
Table 3. Summary of the Estimand Attributes of the Sensitivity Analysis of the Primary Efficacy Endpoint among the PP Population

	Attributes of the Estimand				
Estimand	Treatment	Endpoint	Population	Intercurrent Events	Statistical Summary
Primary efficacy endpoint of HiSCR at Week 16	Risankizumab 180 mg / risankizumab 360 mg / Placebo	Achievement of HiSCR at Week 16 without the initiation of any antibiotics for HS-related infections and without discontinuation of study drug due to lack of efficacy	Patients with moderate to severe HS who have Baseline AN count ≥ 5, and have Baseline draining fistula count ≤ 20.	The intercurrents of either initiation of any antibiotics for HS-related infections or discontinuation of study drug due to lack of efficacy are included in the endpoint attribute using composite variable strategy. No other intercurrent event is considered.	Difference in proportion of subjects achieving HiSCR at Week 16 between each risankizumab dose and placebo

9.4 Secondary Efficacy Analyses

9.4.1 Key Secondary Efficacy Endpoints

The ranked secondary endpoints are as defined in Section 3.2.

[figure not shown]

9.4.2 Main Analyses of Key Secondary Efficacy Endpoints

Ranked secondary efficacy endpoints will be tested between each risankizumab dose and placebo in a hierarchical order only if the null hypothesis of the primary endpoint for the corresponding risankizumab dose has been rejected.

The corresponding null hypotheses for ranked secondary endpoints with respect to each risankizumab dose are:

- 1. There is no difference between each risankizumab dose and placebo, in the proportion of subjects achieving NRS30 in PGA Skin Pain at Week 8 among subjects with Baseline NRS ≥ 3.
- 2. There is no difference between each risankizumab dose and placebo, in the proportion of subjects achieving NRS30 in PGA Skin Pain at Week 16 among subjects with Baseline NRS ≥ 3.
- 3. There is no difference between each risankizumab dose and placebo, in the proportion of subjects who experience flare during Period A.
- 4. There is no difference between each risankizumab dose and placebo, in change from Baseline in DLQI at Week 16.
- 5. There is no difference between each risankizumab dose and placebo, in change rom Baseline in HS-related worst swelling assessed based on the HSSA at Week 16.
- 6. There is no difference between each risankizumab dose and placebo, in change from Baseline in HS-related worst odor assessed based on the HSSA at Week 16.
- 7. There is no difference between each risankizumab dose and placebo, in change from Baseline in HS-related worst drainage—assessed based on the HSSA at Week 16.

Categorical endpoints will be analyzed, using the CMH test adjusting for the actual values of stratification factors. NRI-C will be the primary approach to handle missing data.

Continuous endpoints will be analyzed based on the fixed term of treatment from an MMRM model including the Baseline value and observed measurements at all post-baseline visits, adjusting for the fixed effects of treatment, actual values of stratification factors, visit and treatment-by-visit interaction as covariates.

For the first and second ranked secondary endpoint of HS-related skin pain, any measurements under the impact of analgesic use for HS-related skin pain will be handled as follows:

- Prohibited analgesic (including opioids): A subject will be counted as a non-responder from the day that the subject initiates prohibited analgesic to 5 days after the end of such analgesic use.
- Protocol-allowed analgesic use:
 - A subject who enter the study without concomitant analgesic will be counted as a non-responder from the day that the subject initiates a protocol-allowed analgesic to 2 days after the end of such analgesic use.
 - A subject who entered the study on a stable dose of a protocol-allowed concomitant analysis will be counted as a non-responder from the first day of an analysis dose increase to 2 days after the end of the dose increase.

The attributes of the estimands corresponding to the ranked secondary efficacy endpoints are summarized in Table 4.

[figure not shown]

Table 4. Summary of the Estimand Attributes of the Ranked Secondary Efficacy Endpoints

	Attributes of the Estimand				
Estimand	Treatment	Endpoint	Population	Intercurrent Events	Statistical Summary
Ranked secondary endpoint of NRS30 at Week 8	Risankizumab 180 mg / risankizumab 360 mg / Placebo	Achievement of NRS30 in PGA Skin Pain at Week 8 without the initiation of any antibiotics for HS-related infections, without the impact of analgesics for HS-related skin pain, and without discontinuation of study drug due to lack of efficacy	Patients with moderate to severe HS among Baseline NRS ≥ 3	The intercurrents of either initiation of any antibiotics for HS-related infections, under the impact of analgesics for HS-related skin pain, or discontinuation of study drug due to lack of efficacy are included in the endpoint attribute using composite variable strategy.	Difference in proportion of subjects achieving NRS30 at Week 8 between each risankizumab dose and placebo
Ranked secondary endpoint of NRS30 at Week 16	Risankizumab 180 mg / risankizumab 360 mg / Placebo	Achievement of NRS30 in PGA Skin Pain at Week 16 without the initiation of any antibiotics for HS-related infections, without the impact of analgesics for HS-related skin pain, and without discontinuation of study drug due to lack of efficacy	Patients with moderate to severe HS among Baseline NRS ≥ 3	The intercurrents of either initiation of any antibiotics for HS-related infections, under the impact of analgesics for HS-related skin pain, or discontinuation of study drug due to lack of efficacy are included in the endpoint attribute using composite variable strategy.	Difference in proportion of subjects achieving NRS30 at Week 16 between each risankizumab dose and placebo

[figure not shown]

Table 4. Summary of the Estimand Attributes of the Ranked Secondary Efficacy Endpoints (Continued)

	Attributes of the Estimand						
Estimand	Treatment	Endpoint	Population	Intercurrent Events	Statistical Summary		
Ranked secondary endpoint of flare during Period A	Risankizumab 180 mg / risankizumab 360 mg / Placebo	Experiencing flare during Period A	Patients with moderate to severe HS	No intercurrent event is considered.	Difference in proportion of subjects experiencing flare during Period A between each risankizumab dose and placebo		
Ranked secondary endpoint of change from Baseline in DLQI at Week 16	Risankizumab 180 mg / risankizumab 360 mg / Placebo	Change from Baseline in DLQI at Week 16	Patients with moderate to severe HS	Subjects' observations after the intercurrents of either initiation of any antibiotics for HS-related infections or discontinuation of study drug due to lack of efficacy will be considered as missing and handled by MMRM.	Difference in change from Baseline in DLQI at Week 16 between each risankizumab dose and placebo		
Ranked secondary endpoint of change from Baseline in HS-related worst swelling at Week 16	Risankizumab 180 mg / risankizumab 360 mg / Placebo	Change from Baseline in HS- related worst swelling at Week 16	Patients with moderate to severe HS	Subjects' observations after the intercurrents of either initiation of any antibiotics for HS-related infections or discontinuation of study drug due to lack of efficacy will be considered as missing and handled by MMRM.	Difference in change from Baseline in HS-related worst swelling at Week 16 between each risankizumab dose and placebo		

[figure not shown]
[figure not shown]

Table 4. Summary of the Estimand Attributes of the Ranked Secondary Efficacy Endpoints (Continued)

	Attributes of the Estimand					
Estimand	Treatment	Endpoint	Population	Intercurrent Events	Statistical Summary	
Ranked secondary endpoint of change from Baseline in HS-related worst odor at Week 16	Risankizumab 180 mg / risankizumab 360 mg / Placebo	Change from Baseline in HS- related worst odor at Week 16	Patients with moderate to severe HS	Subjects' observations after the intercurrents of either initiation of any antibiotics for HS-related infections or discontinuation of study drug due to lack of efficacy will be considered as missing and handled by MMRM.	Difference in change from Baseline in HS- related worst odor at Week 16 between each risankizumab dose and placebo	
Ranked secondary endpoint of change from Baseline in HS-related worst drainage at Week 16	Risankizumab 180 mg / risankizumab 360 mg / Placebo	Change from Baseline in HS- related worst drainage at Week 16	Patients with moderate to severe HS	Subjects' observations after the intercurrents of either initiation of any antibiotics for HS-related infections or discontinuation of study drug due to lack of efficacy will be considered as missing and handled by MMRM.	Difference in change from Baseline in HS- related worst drainage at Week 16 between each risankizumab dose and placebo	

